##### **8.4.3.2. Clinical Laboratory Evaluations**

For the continuous laboratory parameters, descriptive statistics will be presented for values collected at all study visits as indicated in [Table 1](#).

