### 3.5. Stopping Rules

The investigator reserves the right to terminate the study in the interests of patient safety and welfare. The Sponsor reserves the right to terminate the study at any time for administrative reasons.

Patients will also be discontinued from the study if they meet the following criteria:

- ALT or AST  $> 3 \times$  ULN with (or the appearance of) fatigue, nausea, vomiting, right upper quadrant pain or tenderness, fever, rash, and/or eosinophilia  $> 5\%$
- ALT or AST  $> 8 \times$  ULN
- ALT or AST  $> 5 \times$  ULN for more than 2 weeks
- ALT or AST  $> 3 \times$  ULN and bilirubin  $> 2 \times$  ULN or INR  $> 1.5$

For patients meeting the above criteria, the investigator will arrange for the patient to return to the investigational site as soon as possible (within 24 hours of notice of abnormal results) for repeat assessment of ALT, AST, bilirubin, and alkaline phosphatase (ALP), detailed history, and physical examination. Patients will be followed until all abnormalities have normalized (in the investigator's opinion) or returned to the baseline state. If the patient is unable to return to the investigational site, repeat assessments may be performed at a local laboratory.

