#### 6.1.5. Clinical Laboratory Assessments

Blood samples for hematology and chemistry assessments and urine sample for urinalysis will be collected during Visit 1 (Day 1), all monthly & quarterly visits, and Visit 7 (End of Study) or Early Withdrawal.

- Hematology: hemoglobin, hematocrit, total and differential leukocyte count, red blood cell (RBC), and platelet count.
- Chemistry: albumin, blood urea nitrogen (BUN), creatinine, total bilirubin, alkaline phosphatase (ALP), aspartate transaminase (AST), alanine transaminase (ALT), sodium ( $Na^+$ ), potassium ( $K^+$ ), chloride ( $Cl^-$ ), lactate dehydrogenase (LDH), uric acid, glucose, and calcium.
- Urinalysis: pH, specific gravity, protein, glucose, ketones, bilirubin, blood, nitrite, leukocyte esterase, and urobilinogen. If protein, occult blood, nitrite, or leukocyte esterase values are out of range a microscopic examination will be performed.

A urine dipstick pregnancy test will be performed on all female post-menarchal patients during at Visit 1 and Visit 7 (End of Study) or Early Withdrawal.

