### 8.2. Sample Size Determination

The sample size is based on successful completion of INS011-17-103, with a maximum of 30 patients.

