### 8.4. Statistical Analyses

This section presents a summary of the planned statistical analyses. A Statistical Analysis Plan (SAP) that describes the details of the analyses to be conducted will be finalized prior to database lock.

Summary statistics will be provided for the variables described as follows. For continuous variables, these statistics will typically include the number of patients, mean, standard deviation, median, minimum, and maximum. For categorical variables, these statistics will typically include the number and percentage of patients in each category.

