##### **8.4.3.4. Electrocardiograms**

For the continuous ECG parameters, descriptive statistics will be presented for values collected at each visit, and for the changes from Baseline to End of Study/Early Withdrawal.

Additionally, the number and percentage of patients will be presented as shift tables for the overall interpretation from Screening (normal or abnormal, not clinically significant [NCS]) to End of Study/Early Withdrawal (normal; abnormal, NCS; or abnormal, clinically significant [CS]).

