#### **8.4.5. Missing Data**

There will be no imputation of the missing values. All assessments will be conducted based on all the observed data.

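### By-visit ALT/AST means leave out patients removed under 3.5, so later means can understate on-treatment elevation and can decline with nobody improving

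*Combined protocol and SAP*

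**What the plan says.** - **Removal.** Section 3.5: "Patients will also be discontinued from the study if they meet the following criteria". The criteria are ALT or AST above 3x ULN with listed symptoms or eosinophilia, above 5x for more than two weeks, above 8x, or above 3x together with bilirubin above 2x or INR above 1.5. After that, "Patients will be followed until all abnormalities have normalized (in the investigator's opinion) or returned to the baseline state".
- **Sampling.** Section 6.1.5 takes blood at Visit 1, "all monthly & quarterly visits, and Visit 7 (End of Study) or Early Withdrawal". A removed patient should therefore have an exit sample. Table 1 gives Early Withdrawal its own column, apart from Visit 7.
- **Laboratory summary.** Section 8.4.3.2: "For the continuous laboratory parameters, descriptive statistics will be presented for values collected at all study visits as indicated in" Table 1. It does not say where Early Withdrawal or unscheduled values are reported.
- **Statistics shown.** Section 8.4: "these statistics will typically include the number of patients, mean, standard deviation, median, minimum, and maximum".
- **Missing data.** Section 8.4.5: "There will be no imputation of the missing values. All assessments will be conducted based on all the observed data".
- **Contrast.** For ECGs, section 8.4.3.4 adds statistics "for the changes from Baseline to End of Study/Early Withdrawal". The laboratory section has no counterpart.
- **Other displays.** The synopsis plans change from baseline and shifts out of the normal range for all patients. Section 8.1 adds mean or median change from baseline and a listing of out-of-limit values. Section 8.4.1.1 tabulates reasons for withdrawal, and 8.4.3.1 summarises adverse events leading to discontinuation.

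**The concern.** For ALT and AST, the variable being summarised also helps decide who is left to be summarised. A patient whose value triggers 3.5 contributes to visits up to removal and to no scheduled visit after it. The hepatic follow-up that 3.5 requires falls outside the Table 1 visits, so by default it does not enter the by-visit tables.

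This matters because the objective is long-term safety and section 8.1 makes change from baseline over time a main safety summary. Transaminase elevation is named in section 6.1.8.1 as an adverse event of special interest, so the signal is foreseeable. A reader who sees mean ALT come down after the early visits could take it for adaptation to the drug when it shows only that affected patients have left.

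**Working it through.** The plan derives no laboratory figure, and its sample size is a cap ("The sample size is based on successful completion of INS011-17-103, with a maximum of 30 patients"), so there is no stated number to reproduce. The check is on the mechanism and its possible size.

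**1. Arithmetic for one visit.** From the documents: N = 30, and ALT/AST multiples of 3, 5 and 8 x ULN. Assumed: the remaining patients sit at a constant 0.7x ULN, and k patients reach x times ULN and are then removed.

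Visit mean before removal = ((30 − k) × 0.7 + k × x) / 30. Visit mean after removal = 0.70.

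| k removed | x = 8 | x = 5 |
|---|---|---|
| 1 | (20.3 + 8)/30 = 0.94 | (20.3 + 5)/30 = 0.84 |
| 2 | (19.6 + 16)/30 = 1.19 | (19.6 + 10)/30 = 0.99 |
| 3 | (18.9 + 24)/30 = 1.43 | (18.9 + 15)/30 = 1.13 |

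In every cell the next visit reads 0.70 with no patient improving. If the others are instead at 0.4x to 0.8x ULN and one patient is removed just above 3x, 5x or 8x (3.1, 5.1, 8.1), the mean drops by between 9% (0.877 to 0.800) and 39% (0.657 to 0.400).

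**2. Chance that it happens at all.** The documents give no rate for meeting 3.5. With an assumed per-patient risk p, P(at least one of 30) = 1 − (1 − p)^30, which is 26%, 60%, 79% and 96% for p = 1%, 3%, 5% and 10%.

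**3. Does the mean have to fall?** A simulation used 30 patients, 20,000 repeats, and visits at Weeks 0, 4, 8, 12, 24, 36 and 48. Assumed: typical ALT 0.5x ULN; affected patients have a persistent 12-fold rise; removal follows a single 5x threshold, a simplification of 3.5. Means are in multiples of ULN.

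| Scenario | Observed mean | Full-cohort mean, Week 48 |
|---|---|---|
| 10% affected, all from Week 4 | 0.53, 1.11, 0.66, 0.61, 0.59, 0.58, 0.58 | 1.11 |
| 10% affected, random onset | rises 0.53 to 0.70 | 1.11 |
| 10% affected, random onset, 30% upward drift in everyone | rises 0.53 to 0.86 | 1.44 |
| Nobody affected | flat at 0.53 | 0.53 |

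An apparent recovery occurs in the first scenario. In the second and third the mean rises but understates. In the last nothing changes. The median is little affected: in the first scenario it goes from 0.527 at Week 4 to 0.506 at Week 48.

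**4. Does using the exit value help?** Combining each removed patient's exit value with the others' Week 48 values gives 1.13 in the first scenario and 1.12 in the second, against a full-cohort 1.11 in both. With drift and random onset it gives 1.36 against 1.44. This recovers most of what the observed mean (0.58, 0.70 and 0.86) loses.

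**The case against.** The strongest reply is that a patient removed at 8x ULN does not vanish from the report. The synopsis shifts, the out-of-limit listing, the withdrawal reasons and the summary of adverse events leading to discontinuation would all show that patient. The per-visit n would fall, the median would hardly move, and the maximum would show the peak if it fell on a scheduled visit. This stands, and a reader who infers that removed cases are hidden would be wrong. These displays do not repair the later-visit means, however. A shift to outside normal range does not separate a value just above ULN from one at 8x, and 8.4.3.2 does not carry the shift table over from the synopsis.

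Two further readings are tempting and not supported:

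- *Later means must fall.* They need not, as the simulation shows. What follows is narrower: if removed patients would have stayed above the rest, the observed mean lies below the full-cohort mean.
- *The same holds for vital signs and weight.* Section 3.5 has no criterion on either, so the direct link between value and removal is absent.

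Early removals are also made less likely by the entry rules. Patients have completed INS011-17-103, and 3.2.2 excludes clinically significant liver tests at or above 3x ULN within 14 days. Dose increases remain possible, so the risk is reduced and not removed. In the earlier long-term study, 7 of 52 patients (13.5%) left early, and none of the reasons listed in section 1.3 is a transaminase elevation. That rate would leave about 26 of 30 (45/52 × 30 = 26.0) at the end, but it says nothing about how often 3.5 would be met.

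Finally, section 8.4 calls itself a summary and defers detail to a SAP to be finalised before database lock. No separate SAP is in the supplied text, and it may settle the point.

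**Conclusion.** The concern holds for ALT and AST. Under 3.5, 8.4.3.2 and 8.4.5 taken together, later-visit means describe only patients not yet removed, and removal depends on the value summarised. They can understate on-treatment elevation and can decline without any patient improving.

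With at most 30 patients, a single removal at 8x ULN takes the visit mean from 0.94x to 0.70x (others assumed at 0.7x). Across the assumptions tried, one removal lowers the mean by 9% to 39%. These sizes rest on assumed ALT levels and on at least one patient meeting 3.5. If none does, the tables are unaffected. The gap is also measured against elevation on treatment: if values normalise after the drug is stopped, the gap to an off-treatment mean is smaller.

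This is an inexpensive improvement to the reporting of a foreseeable signal. It does not mean that the study would lose its hepatic safety data.

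**What to change.** In 8.4.3.2 and the SAP, for ALT, AST and bilirubin, over all enrolled patients with a post-baseline value and including Early Withdrawal and unscheduled samples:

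1. Add change from baseline to the last on-treatment value, parallel to the End of Study/Early Withdrawal analysis in 8.4.3.4.
2. Add each patient's worst post-baseline value, and counts above the multiples of ULN already used in 3.5 (3x, 5x and 8x for ALT and AST; 2x for bilirubin). The last value can miss a peak that has begun to come down; the worst value does not.
3. Beside each by-visit mean, print the number still in the study and the cumulative number discontinued under 3.5.
4. State that by-visit means describe remaining patients only.

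Vital signs and weight need no change on this ground. The cost is SAP wording and a few extra table rows. All the data are already collected.

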##### **8.4.3.3. Vital Signs**

For blood pressure, pulse rate, temperature, and respiration rate, descriptive statistics will be presented for values collected at all study visits as indicated in [Table 1](#).

##### **8.4.3.4. Electrocardiograms**

For the continuous ECG parameters, descriptive statistics will be presented for values collected at each visit, and for the changes from Baseline to End of Study/Early Withdrawal.

Additionally, the number and percentage of patients will be presented as shift tables for the overall interpretation from Screening (normal or abnormal, not clinically significant [NCS]) to End of Study/Early Withdrawal (normal; abnormal, NCS; or abnormal, clinically significant [CS]).

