### 3. INVESTIGATIONAL PLAN

#### 3.1. Overall Study Design

This is a multicenter, open-label, flexible dose study designed to assess the long-term safety and tolerability of CBD in doses ranging from 20 mg/kg/day to 40 mg/kg/day in patients with treatment-resistant childhood absence seizures. Patients must have completed INS011-17-103 to be eligible.

The Investigator will ensure that the patients legal representative [parent(s)/caregiver(s)] will receive a copy of the informed consent form for review and provide full informed consent prior to study participation.

Patients should enroll in Long-Term Safety Study (INS011-17-113) after completing Study INS011-17-103 Visit 6 (End of Study) to avoid interruption of the investigational product. Patients will have up to 2 weeks to enroll in INS011-17-113. The first visit (Visit 1) for INS011-17-113 will be after the completion of Visit 6 of INS011-17-103.

Patients will continue to receive CBD treatment for approximately 48 weeks. Patients will remain on their assigned dose or may be titrated up to a higher dose level if the Data Monitoring Committee has approved the higher dose level in INS011-17-103. **If any participant does not enroll within the 2 week window, the patient will not be eligible to enroll into the study.**

The study will consist of a Safety Period (48±2 weeks), Taper Period (10±3 days), and a Follow-up Period (30±5 days). Treatment visits will be scheduled monthly for the first 3 months and then quarterly over the remaining 9 months. All patients will complete a Visit 7 (End of Study) or Early Withdrawal Visit regardless of when they stop treatment/complete the study. A Follow-Up telephone call (Visit 9) will occur 30 days after the end of either the End of Study (Visit 7) or Early Withdrawal.

In this study, all patients will be dosed as follows:

- Once the informed consent for INS011-17-113 is provided within the required time frame, initially the patient will receive the same dose as was administered during INS011-17-103. If tolerability issues occurred during INS011-17-103, the dose can be decreased if the dose was greater than 20 mg/kg/day. If the patient received 20 mg/kg/day and the physician wants to decrease the dose, the patient should be discontinued.

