**Figure 1: Study Design Schematic**

### 3.2. Patient Selection

#### 3.2.1. Inclusion Criteria

Patients must meet all of the following inclusion criteria:

1. Completed all activities through Visit 6 (End of Study) of INS011-17-103.
2. Patient and/or parent(s)/caregiver(s) fully comprehend the informed consent form (ICF) and assent form, understand all study procedures, and can communicate satisfactorily with the investigator and study coordinator, in accordance with applicable laws, regulations, and local requirements.
3. A female patient is eligible to participate in the study if she is:
  - a. Premenarchal, or
  - b. Of childbearing potential with a negative urine pregnancy test at the Screening Visit. If sexually active, she must agree to fulfill one of the following requirements:
    - i. Complete abstinence from intercourse for  $\geq$  4 weeks prior to administration of the first dose of the investigational product, throughout the Safety Period, and 4 weeks after completion or premature discontinuation from the investigational product, and agreement to use a double barrier method if she becomes sexually active.
    - ii. Use of acceptable methods of contraception throughout the study and 4 weeks after completion or premature discontinuation from investigational product. The acceptable method of contraception is double barrier method (i.e., condom plus spermicide or a condom plus intrauterine device [IUD], diaphragm, or stable hormonal contraceptive use for at least 3 months before screening and through 14 days after study completion).
4. A sexually active male patient or partner of enrolled patient must be willing to use acceptable methods of contraception throughout the study and for 4 weeks after completion of study participation or discontinuation from investigational product. The acceptable methods of birth control are abstinence or double barrier birth control (i.e., condom plus spermicide or a condom plus one of the methods listed in criterion #3).
5. In the opinion of the investigator, the parent(s)/caregiver(s) is (are) willing and able to comply with the study procedures and visit schedules, including venipuncture, and the visit schedules.

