### 4.4. Selection and Timing of Dose for Each Patient

Once the informed consent for INS011-17-113 is provided, patients will initiate this long-term safety study on the final dose of CBD administered during the study INS011-17-103 Visit 6 (End of Study). Subsequently, the dose may be increased to a maximum of 40 mg/kg/day only if the higher dose level has been approved by the Data Monitoring Committee in INS011-17-103.

Patients will take each dose approximately every 12 hours with food in order to ensure consistent plasma levels are achieved. The date and time of all investigational product administrations will be documented in the case report form (CRF).

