#### 6.1.4. Electrocardiograms

A resting 12-lead ECG will be conducted for every patient at Visit 1 (Day 1), all monthly & quarterly visits, and Visit 7 (End of Study) or Early Withdrawal.

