## 8. STATISTICS

### 8.1. Safety Endpoints

Changes in safety endpoints will be reported as mean/median change from baseline at relevant time points and as a listing of events that fall outside normal limits. Baseline is defined as Visit 6 of INS011-17-103.

- Incidence, type, and severity of AEs and serious adverse events (SAEs) associated with Cannabidiol Oral Solution (i.e., treatment-emergent adverse events [TEAEs]).
- Changes from baseline in vital signs, physical exam (including height and weight), ECG findings, and laboratory values (hematology, chemistry, and urinalysis).
- Changes from baseline in neurological exam.

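### The ECG shift table starts at an undefined Screening visit instead of the defined Baseline, has no starting row for a clinically significant abnormality, and uses only the final ECG

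*Combined protocol and SAP*

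**What the plan says.** Section 8.4.3.4 has two sentences on ECG analysis. For continuous parameters, "descriptive statistics will be presented for values collected at each visit, and for the changes from Baseline to End of Study/Early Withdrawal". For the overall interpretation it plans "shift tables for the overall interpretation from Screening (normal or abnormal, not clinically significant [NCS]) to End of Study/Early Withdrawal". The starting categories are normal and abnormal NCS; the ending categories are these two plus abnormal CS.

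Section 8.1 and the synopsis fix one reference point for change in safety endpoints, ECG findings included: "Baseline is defined as Visit 6 of INS011-17-103".

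Table 1 begins at Visit 1 (Day 1) and Section 7 describes no earlier visit. Section 6.1.4 states: "A resting 12-lead ECG will be conducted for every patient at Visit 1 (Day 1"; it goes on to require an ECG at every monthly and quarterly visit and at Visit 7 or Early Withdrawal. The only other mention of a screening visit is inclusion criterion 3b, "Of childbearing potential with a negative urine pregnancy test at the Screening Visit", which is not defined either.

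On growth, Section 8.1 lists change from baseline in height and weight. Section 8.4.3.5 counts normal and abnormal examination results. No age- and sex-standardised measure is mentioned.

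**The concern.** Two adjacent sentences on the same data use different starting labels, and only one of them is defined. The table therefore cannot be programmed from the text without a guess, and the possible guesses give different tables.

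The uneven categories add a second gap. A patient whose starting ECG is abnormal CS can be placed in no row, so neither persistence nor resolution can be shown.

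The third gap is timing. ECGs are taken throughout the 48 weeks, but the only summary specified for the interpretation looks at the last one. The sole objective is long-term safety and tolerability, and a finding that appears mid-study and then resolves is part of that picture.

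For weight, the sponsor's own earlier studies report an increase as a drug-related event. In growing children, raw change over 48 weeks mixes that signal with ordinary growth.

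**Working it through.** The plan states no ECG abnormality rate, so there is no figure of its own to reproduce. The check is a comparison of passages, a count from the schedule, and some scale under stated assumptions.

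**1. What Screening could mean**

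| Reading | Relation to this study | Consequence |
|---|---|---|
| A screening ECG in INS011-17-103 | Parent study; its schedule is not in the document | Possibly before cannabidiol (CBD); cannot be confirmed |
| Visit 6 of INS011-17-103 | The defined Baseline | Agrees with Section 8.1 |
| Visit 1 here | Has its own ECG (Section 6.1.4) | Can follow Visit 6 by up to two weeks: "Patients will have up to 2 weeks to enroll in INS011-17-113" |

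No passage says which is meant. The shift bullets in the synopsis cover laboratory values, vital signs, neurological and physical examinations, but not ECG.

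**2. Cells**

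- As written: 2 starting x 3 ending categories = 6.
- Full grid: 3 x 3 = 9.
- Missing: 9 - 6 = 3, all in the abnormal CS starting row.

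Exclusion criterion 4 (Section 3.2.2) covers clinically significant cardiovascular disease in general; there is no ECG criterion. If a fraction p of patients started with a CS ECG (assumed), the chance that at least one of 30 has no row is 1 - (1 - p)^30: 0% at p = 0, 45% at 2%, 79% at 5%, 96% at 10%.

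**3. ECGs left out**

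Scheduled ECGs after the Visit 6 baseline are Day 1 and Weeks 4, 8, 12, 24, 36 and 48, which makes 7. The table uses one (Week 48) and leaves out 6. If Visit 1 were the start, 5 of 6 would be left out. For 30 completers, a worst-value table would draw on up to 30 x 7 = 210 ECGs instead of 30.

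**4. Scale for a transient finding (assumptions only)**

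- Present at one of the seven visits, each equally likely: the final ECG shows it with chance 1/7 = 14%.
- Present at any two of seven: C(6,1)/C(7,2) = 6/21 = 29%.
- Independent chance q of a CS reading at each ECG: P(any of 7) = 1 - (1 - q)^7, and the share of affected patients not CS at the last ECG is 1 - q/P(any).

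| Assumed q | P(any of 7) | Expected of 30, any visit | Expected of 30, last visit | Share not shown as CS |
|---|---|---|---|---|
| 1% | 6.8% | 2.0 | 0.3 | 85% |
| 2% | 13.2% | 4.0 | 0.6 | 85% |
| 5% | 30.2% | 9.0 | 1.5 | 83% |

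**5. Weight**

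Section 1.3 lists weight increase among the dose-dependent events in the earlier PK study. In the earlier long-term study it was a drug-related event in 4 subjects, with gains from a little over 2 lb to about 7 lb. At 0.4536 kg per lb that is about 0.9 to 3.2 kg. If ordinary growth is 1.5 to 5 kg a year (assumed), 48 weeks contribute 48/52 x 1.5 = 1.4 kg to 48/52 x 5 = 4.6 kg. The ranges overlap, so raw change cannot separate them.

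**The case against.** **The label is a slip with an obvious reading.** Baseline is defined once and expressly covers ECG findings, so Visit 6 is the natural default. The study also has a screening step: Table 1 places consent and eligibility review in the two weeks after Visit 6, and Sections 9.2 and 9.3 mention screening and screen failures. On that view the choice lies between Visit 6 and Visit 1, at most two weeks apart. This makes the pre-CBD reading less likely, but it does not settle which ECG goes into the table.

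**A CS ECG at entry is unlikely.** The cardiovascular exclusion and the investigator's general discretion both work against it. That stands as to likelihood, but neither rules it out.

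**The other ECGs are not discarded.** Continuous parameters are summarised at each visit, ECGs are listed by visit, out-of-limit findings are listed, and an ECG finding may be reported as an adverse event and tabulated. The synopsis also allows descriptive summaries where appropriate. All of this stands. A reader might infer that a transient abnormality would vanish from the report, and the documents do not support that. What is missing is a specified summary of the interpretation at any visit but the last.

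**The Visit 6 baseline.** A reader might also infer that it is an error because patients are already on CBD. It is not: Visit 6 is a proper baseline for an extension. The protocol makes the on-treatment status plain, since "initially the patient will receive the same dose as was administered during INS011-17-103" and, in Section 4.4, "patients will initiate this long-term safety study on the final dose of CBD administered during the study INS011-17-103 Visit 6 (End of Study". Observed values are summarised beside change, so a stable elevation remains visible. Labelling the tables as on-treatment is optional.

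**Growth.** Lack of standardisation is an omission, not a contradiction, and summaries by age cohort are planned where appropriate. However, this protocol defines no age cohorts.

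**Conclusion.** The ECG point holds. The shift table has a starting point that the protocol does not define and that departs from the Baseline used one sentence earlier. It provides 6 of 9 cells, and it leaves out 6 of a completer's 7 post-baseline ECGs.

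The counts of cells and visits come from the text. The 6 of 7 assumes Visit 6 is the start and that the Day 1 ECG is a separate recording. The document does not show the parent study's schedule, although defining ECG change from Visit 6 implies an ECG there. The percentages in steps 2 and 4 illustrate scale only; no frequency of ECG abnormality is claimed.

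Standardised growth measures are a secondary improvement. A comparison with pre-CBD values is optional and depends on INS011-17-103 holding them, which the document does not show.

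Severity is minor to moderate. The analysis is descriptive with no formal inference, enrolment is capped at 30, and Section 8.4 leaves details to a SAP due before database lock, where all of this can be settled.

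**What to change.** In Section 8.4.3.4, or in the SAP:

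- Replace Screening with the defined Baseline (Visit 6 of INS011-17-103).
- Use the same three categories (normal; abnormal NCS; abnormal CS) at start and end.
- Keep the End of Study/Early Withdrawal shift and add one from Baseline to the worst post-baseline interpretation, stating whether the Day 1 ECG counts as post-baseline.
- Show the number of patients without an ECG at either end, since nothing is imputed.

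The same undefined visit name in inclusion criterion 3b should be reconciled with Table 1.

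Secondary: report weight, height and BMI as age- and sex-standardised z-scores beside raw change, with the growth reference named in the SAP.

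The cost is a few words, one row, one extra ECG table and derived growth variables. No new visits are needed, and the Visit 6 baseline already requires data from the parent study. The drawback is that a worst-value shift will tend to show more abnormalities than an end-of-study shift. The two should stand side by side, with a note that there is no control arm and that other antiepileptic treatment may change during the study (Section 3.4).
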